9.11. CONSTRAINTS RELATED TO THE RESEARCH AND POSSIBLE COMPENSATION OF PARTICIPANTS

As ECOLIFT study does not require any additional clinical visit or any additional invasive examination than normal clinical practice, there won't be any compensation for participants.

10. MANAGEMENT OF ADVERSE EVENTS AND NEW DEVELOPMENTS

10.1. DURING THE CLINICAL TRIAL

Adverse events / undesirable effects / incidents will be declared to the various circuits of health vigilance applicable to each product or practice concerned (care vigilance, pharmacovigilance, materiovigilance, haemovigilance, cosmetovigilance ...) in accordance with the regulations in force.

Registrants should specify that the participant is included in a clinical trial and accurately identify the clinical trial concerned.

If the investigator becomes aware of a breach of patient safety in the course of the research, he must inform the sponsor without delay.

10.2. FROM THE SNDS

The SNDS is a database using anonymous individual information without any spontaneous reporting. Study outcomes will be reported in aggregate in the final study report, and no individual or expedited reporting is required, according to the EMA Guideline on good pharmacovigilance practices cited above (GVP VI*), as well as the ENCePP Guide on Methodological Standards in Pharmacoepidemiology.

* The latest revision of the Guideline on good pharmacovigilance practices (GVP) Module VI – Collection, management and submission of reports of suspected adverse reactions to medicinal products (Rev 2) from EMA (coming into effect 22 Nov 2017) specifies: For Non-interventional post-authorisation studies based on secondary use of data (VI.C.1.2.1.2): "The design of such studies is characterised by the secondary use of data previously collected from consumers or healthcare professionals for other purposes. Examples include medical chart reviews (including following-up on data with healthcare professionals), analysis of electronic healthcare records, systematic reviews, meta-analyses. For these studies, the submission of suspected adverse reactions in the form of ICSRs is not required. All adverse events/reactions collected for the study should be recorded and summarised in the interim safety analysis and in the final study report unless the protocol provides for different reporting due to justification".

11. STATISTICAL ASPECTS

11.1. CALCULATION OF STUDY SIZE

In the SNDS, the study size will depend on the number of patients initially recruited. The expected number of patients will thus be for:

- **PUL Cohort:** 80 patients with PUL;
- TURP/Laser Cohort: 80 patients for the TURP or laser surgery
- **SNDS Cohort:** 1200 patients distributed between 400 matched TURP patients, 400 matched HLE patients and 400 matched HLV patients.

80 patients (in each of the PUL and TURP cohorts) will allow 95% confidence intervals with a precision:

- between 7% and 11% for observed proportions between 10% and 50%
- between 13% and 26% for observed means with coefficient of variation between 0.6 and 1.2.

Furthermore, 80 patients in each PUL and TURP cohorts is largely enough to answer to the primary economic objective (cost-effectiveness ratio, expressed as incremental cost/avoided complications) with a power of 80% and an alpha risk of 5%. In fact, according to the Glick formula¹, the needed number to treat to answer this question is about 40.

400 patients in each of the 3 subgroups of the SNDS cohort will allow 95% confidence intervals with a precision:

- between 3% and 5% for observed proportions between 10% and 50%,
- between 6% and 12% for observed means with coefficient of variation between 0,6 and 1,2.

11.2. STATISTICAL METHODS EMPLOYED

11.2.1. GENERALITIES

Statistical analysis will be performed using SAS® software (SAS Institute, latest current version, North Carolina, USA). Qualitative and ordinal variables will be summarized by frequencies and proportions of each modality, taking into account missingness as a modality. Continuous variables will be summarized by size, number of patients with missing data, arithmetic mean, standard deviation, median, interquartile ranges and extreme values. Confidence intervals will be estimated using Normal approximation for quantitative and qualitative relevant parameters, or bootstrapping method for costs when count < 100 patients.

Standardized mean differences (*Rosenbaum*, *Rubin*, 1985) will be estimated to measure the effect size of quantitative and qualitative baseline characteristics between groups (PUL and TURP cohorts, matched patients of PUL and SNDS cohorts).

For confidence intervals, 2-sided confidence level of 95% will be used. For all tests, a 2-sided significance level of 5% will be used:

- Proportions will be compared between two independent groups using Pearson's Chi-2 test (or Fisher's exact test when expected counts are < 5)
- Means will be compared between two independent groups using Student's t-test when normal distribution is followed (or Mann-Whitney's test when normal distribution is not followed)
- Occurrence of events (retreatment, urinary symptoms) will be estimated across time using Kaplan-Meier estimator and compared between groups with logrank test.
- Adjusted comparisons between PUL and the TURP/Laser cohorts and between PUL and SNDS cohorts will be
 performed in intention-to-treat analysis using linear regression model when it involves quantitative variables,
 and using logistic regression model adjusted on potential confounders when it involves qualitative variables.

[figure not shown]
A Statistical Analysis Plan (SAP) will be developed and will be validated before the analyses.

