1.1.2.2. UROLIFT

Prostatic urethral lift (PUL) has been developed as a minimally invasive alternative to TURP with no need of general anaesthesia, less need of urinary catheter and less exposure to post-operative complications. Two randomized studies have been conducted to assess the efficacy and safety of this procedure.

The LIFT study is a randomized controlled trial (North America and Australia) comparing Urolift with sham procedure. Roehrborn et al. reported rapid improvement in urinary symptoms, quality of life (QoL) and flow rate that was durable to 5 years. IPSS and QoL improvements in this study were respectively 36% and 50% and surgical retreatment rate was 13.6%. Sexual function was stable over 5 years with no de novo, sustained erectile or ejaculatory dysfunction. (4)

The BPH6 study is a European multicentric randomized controlled trial comparing Urolift with TURP. After one year follow-up, Sonksen et al. reported better improvement of the composite quality of life endpoint in the Urolift group. Gratzke et al reported the 2-year outcomes of the same study. Change in IPSS and Qmax in the TURP arm were superior to the PUL arm but PUL resulted in a superior quality of recovery and ejaculatory function preservation. It resulted in better performance of Urolift on the composite BPH6 index (including IPSS, Sexual Health Inventory for Men (SHIM), Male Sexual Health Questionnaire for Ejaculatory Dysfunction (MSHQ-EjD), Incontinence Severity Index (ISI), Quality of Recovery visual analogue score (QoR VAS), and the Clavien–Dindo classification of adverse events. (5)

In summary, PUL resulted in urinary symptom improvement that remained inferior to TURP but that were durable for 5 years. PUL preserved overall quality of life better than TURP especially with regard to sexual quality of life and quality of recover.

Given these results, Urolift has been recommended by the EAU guidelines (EAU guidelines for management of non neurogenic male LUTS; https://uroweb.org/guideline/treatment-of-non-neurogenic-male-luts/) and has been recognized by the French authorities (HAS) (Appendix 1).

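### Normal-approximation intervals have no small-count fallback, so 95% intervals for uncommon secondary events in 80 patients would be unreliable, and 0/80 would be reported as 0% to 0% (minor)

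*Protocol*

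**What the plan says.** Section 11.2.1 (Generalities) gives one rule for intervals: "Confidence intervals will be estimated using Normal approximation for quantitative and qualitative relevant parameters". Its only exception is a bootstrap for costs with fewer than 100 patients. It adds: "For confidence intervals, 2-sided confidence level of 95% will be used".

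For tests of proportions, the same section moves from Pearson's chi-squared to "Fisher's exact test when expected counts are < 5". It also assigns event occurrence (retreatment, urinary symptoms) to Kaplan-Meier estimation with a logrank comparison, and names no separate interval method for those estimates.

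Section 11.1 gives the planned precision. "80 patients (in each of the PUL and TURP cohorts) will allow 95% confidence intervals with a precision" introduces the range "between 7% and 11% for observed proportions between 10% and 50" per cent. For the 400-patient SNDS subgroups the range is "between 3% and 5% for observed proportions between 10% and 50" per cent.

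Section 11.2.4 describes complications by number and type. It also counts patients hospitalised for urinary infection, retention or urethral stricture over three years. Section 11.2.3 obtains the interval for the primary cost-effectiveness ratio by bootstrap.

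**The concern.** The Wald interval takes its variance from the observed proportion. With few events that variance is badly estimated, and with no event it is zero. Section 11.2.1 allows for small numbers twice, in the bootstrap for costs and in the Fisher fallback for tests, but not in the intervals for proportions. A table could therefore pair a Fisher p-value with an interval that is not valid at the same counts.

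Some outcomes in section 11.2.4 could be sparse in 80 men once complications are split by type or hospitalisations by cause. A PUL complication type seen in none of 80 patients would carry an interval of 0% to 0%, which overstates what 80 patients can show. With one to three events the lower limit would be negative.

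**Working it through.** **Inputs.** n = 80 per clinical cohort and n = 400 per SNDS subgroup (section 11.1); two-sided 95%, z = 1.96 (section 11.2.1). The protocol gives no rates for the uncommon events, so true rates of 1% to 5% are assumed. Section 1.1.2.1 gives 20% to 40% for Clavien-Dindo grade 2 or higher complications with the comparator techniques.

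**The plan's own precision figures.** Half-width = 1.96 × √(p(1−p)/n).
- n = 80: 1.96 × √(0.10 × 0.90/80) = 6.57%; 1.96 × √(0.50 × 0.50/80) = 10.96%. Stated: 7% and 11%.
- n = 400: 2.94% and 4.90%. Stated: 3% and 5%.

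All four agree after rounding, so section 11.1 needs no change.

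**Coverage at n = 80.** The miss rate is the binomial probability, summed over x = 0 to 80, of every count x whose interval x/80 ± 1.96 × √(p̂(1−p̂)/80) excludes the true rate.

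Example at a true rate of 4%: zero events gives 0% to 0%, and one event gives −1.18% to 3.68%. Both exclude 4%. Their probabilities are 3.8% and 12.7%, together 16.5%. Nine or more events add about 0.5%, for a total of 17.0%.

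| True rate | Wald miss rate | Wilson miss rate | Chance of 0/80 |
|---|---|---|---|
| 1% | 44.8% | 4.7% | 44.8% |
| 2% | 20.0% | 2.2% | 19.9% |
| 3% | 9.0% | 3.3% | 8.7% |
| 4% | 17.0% | 4.1% | 3.8% |
| 5% | 9.3% | 6.3% | 1.7% |
| 10% | 10.0% | 3.7% | 0.0% |
| 20% | 6.8% | 3.5% | 0.0% |
| 30% | 5.1% | 3.7% | 0.0% |
| 40% | 5.2% | 5.2% | 0.0% |

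The Wald miss rate oscillates between these points. At 3.68%, where the one-event interval just reaches the true rate, only zero events and a small upper tail miss: 0.9632^80 = 5.0%, plus about 0.3%, or 5.3%. Averaged over 1% to 5%, the miss rate is about 17%. Over 5% to 10% it averages 8.4%, and over 20% to 40% it averages 5.8%. Average Wilson coverage over 1% to 5% is 95.7%, with a minimum of 92.1%.

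**Intervals at small counts, n = 80.**

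| Events | Wald | Wilson | Clopper-Pearson |
|---|---|---|---|
| 0 | 0% to 0% | 0% to 4.58% | 0% to 4.51% |
| 1 | −1.18% to 3.68% | 0.22% to 6.75% | 0.03% to 6.77% |
| 2 | −0.92% to 5.92% | 0.69% to 8.66% | 0.30% to 8.74% |
| 3 | −0.41% to 7.91% | 1.28% to 10.45% | 0.78% to 10.57% |

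The exact upper limit at 0/80 is 1 − 0.025^(1/80) = 4.51%. The Wald lower limit is negative for one to three events, which has probability 72% at a true rate of 2% and 41% at 5%.

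**SNDS subgroups, n = 400.** Wald coverage is 90.7% at 1%, 89.5% at 2% and 92.7% at 5%. The problem is smaller but still present.

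**The case against.** The strongest reply is that the protocol does not say Wald. Wilson's score interval is also a Normal-approximation method, and its half-widths (6.7% and 10.7% at n = 80; 2.95% and 4.88% at n = 400) round to the same figures in section 11.1. That is correct, so section 11.1 cannot settle which is meant. But Wald is the ordinary meaning of the phrase, and nothing in the protocol points to a score or exact interval. A SAP is announced and could state the formula, yet the protocol has already named the method and its only exception.

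The documents do not support four stronger readings:
- A reader might infer that every proportion is affected. The text covers only relevant parameters. Retreatment and urinary-symptom events, which under section 3.2 include the three hospitalisation outcomes, are also assigned to Kaplan-Meier. Section 11.2.4 still describes these as counts of patients, and a plain Normal (Greenwood) interval also has zero width with no events.
- A reader might infer from "no de novo, sustained erectile or ejaculatory dysfunction" in section 1.1.2.2 that zero counts are expected for PUL. That is another trial's result. Here the sexual outcomes are the IIEF15 and MSHQ-EjD questionnaire scores, so no 0/80 proportion follows from it.
- A reader might take surgical retreatment to be rare. Section 1.1.2.2 cites 13.6% at five years, where the Wald miss rate at n = 80 is 7.9%.
- A reader might infer that the reimbursement result is at risk. The primary ratio and net monetary benefit use the bootstrap (section 11.2.3), and tests of proportions have the Fisher fallback.

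**Conclusion.** The point holds as a minor one, limited to intervals for uncommon secondary and descriptive proportions. It rests on two assumptions: that Normal approximation means Wald, and that some reported events have true rates of about 1% to 5%. At the whole-number rates in that range the 95% interval misses the truth about 9% to 45% of the time at n = 80. The 0% to 0% interval at 0/80 needs only the first assumption. At 20% to 40% the miss rate is about 5% to 7%, which is not a material problem. The primary analysis, the between-group tests and the study size are unaffected.

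**What to change.** In section 11.2.1, replace the interval rule for qualitative parameters with wording such as: Confidence intervals for single proportions will be Wilson intervals (Clopper-Pearson when there are very few events, for example fewer than five); intervals for differences in proportions will be Newcombe intervals; Normal approximation is kept for means, and the bootstrap for costs below 100 patients. Add that Kaplan-Meier estimates will not carry a plain Normal interval when events are few.

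The cost is one or two sentences, using standard SAS options, with no new data and no change in sample size. Some intervals become slightly wider and asymmetric. Settling the method before analysis also avoids choosing it after a zero cell has been seen.

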5.2.3. MATCHING CRITERIA

A total of 5 patients will be matched to 1 patient of the PUL cohort for each procedure (TURP, HLE, GLV) according to age, date of the procedure (same month) and a high dimensional disease risk score (hDRS) based on the one-year SNDS information before the surgical procedure. The Disease Risk Score (DRS) estimates the probability of complications occurrence in the absence of the surgery of interest (PUL). DRS will be computed from a multivariable logistic regression model using a large set of variables collected during the one-year period among the SNDS cohort.

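### PUL v SNDS is matched 1:5 within each procedure, but no method named for it uses the matched set; its unadjusted intervals are likely somewhat too wide

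*Protocol*

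**What the plan says.** **Design.** Protocol sections 4.1 and 5.2.3 describe individual matching: "A total of 5 patients will be matched to 1 patient of the PUL cohort for each procedure (TURP, HLE, GLV"), on age, "date of the procedure (same month) and a high dimensional disease risk score (hDRS"). The score is an outcome predictor: "The Disease Risk Score (DRS) estimates the probability of complications occurrence in the absence of the surgery of interest (PUL"). Section 11.1 gives the resulting sizes as "80 patients with PUL" and "1200 patients distributed between 400 matched TURP patients, 400 matched HLE patients and 400 matched HLV patients" (HLV there is presumably the GLV group of section 5.2.3).

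**Analysis.** Section 11.2.1 opens its list of tests with "For all tests, a 2-sided significance level of 5% will be used". The list then contains:
- for proportions, "Proportions will be compared between two independent groups using Pearson's Chi-2 test", or Fisher's exact test;
- for means, Student's t or Mann-Whitney, also for two independent groups;
- for events over time, Kaplan-Meier curves "compared between groups with logrank test";
- for adjusted comparisons, linear or logistic regression. This item names PUL v SNDS expressly, alongside PUL v TURP/laser, and the Data Analysis part of the summary repeats the models. The covariates are described only as potential confounders.

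Matching reappears in the standardized differences before and after matching (sections 11.2.1 and 11.2.2) and in descriptions by matched treatment group (section 11.2.4). No conditional, stratified, mixed or clustered method is named anywhere.

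**The concern.** Matching on age, calendar month and a score that predicts complications is meant to make the members of a set prognostically alike. Their outcomes should therefore be positively correlated, at least for complications. An analysis that treats the PUL patient and his five controls as unrelated overstates the variance of their difference.

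What is at stake is precision. Section 1.3 justifies the SNDS phase partly by the statistical power it brings to PUL against each procedure. If the sets are ignored, some of the precision bought by matching is not used. The log-rank test, which would cover retreatment, is the most exposed: as named, it has no covariates through which the matching variables could enter.

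**Working it through.** **1. The protocol's own figures.** Sizes: 80 × 5 = 400 per procedure and 400 × 3 = 1200. Both agree with section 11.1. Precision, using 1.96·√(p(1−p)/n) for proportions and 1.96·CV/√n for means:

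| n | Proportions 10% and 50% | Stated | Means, CV 0.6 and 1.2 | Stated |
|---|---|---|---|---|
| 80 | 6.57%, 10.96% | 7% to 11% | 13.15%, 26.30% | 13% to 26% |
| 400 | 2.94%, 4.90% | 3% to 5% | 5.88%, 11.76% | 6% to 12% |

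All reproduce after rounding, under independence.

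**2. Variance of the matched difference.** Take 80 sets of one PUL patient and five controls, a common variance σ² and within-set correlation ρ. The variance of one set's difference is

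σ²[1 + (1 + 4ρ)/5 − 2ρ] = 1.2σ²(1 − ρ).

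Over 80 sets the true variance is 1.2σ²(1 − ρ)/80. The independent-groups formula gives σ²/80 + σ²/400 = 1.2σ²/80. The independent-groups standard error is therefore too large by the factor 1/√(1 − ρ). Pooling all 15 controls of a PUL patient gives the same (1 − ρ) factor if ρ is common across procedures.

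**3. Numbers.** The documents give no ρ, so the values below are assumptions. The real alpha is 2[1 − Φ(1.96/√(1 − ρ))]. The half-width illustration uses p = 30%, the middle of the 20% to 40% complication range in section 1.1.2.1.

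| ρ (assumed) | Independent-groups SE too large by | Real alpha of nominal 5% test | 95% half-width ignoring sets | Using sets |
|---|---|---|---|---|
| 0.02 | 1.0% | 0.048 | 11.0 points | 10.9 |
| 0.05 | 2.6% | 0.044 | 11.0 | 10.7 |
| 0.10 | 5.4% | 0.039 | 11.0 | 10.4 |
| 0.20 | 11.8% | 0.028 | 11.0 | 9.8 |
| 0.30 | 19.5% | 0.019 | 11.0 | 9.2 |

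**4. Simulation under no effect.** 80 sets of 1:5, all members of a set sharing the same underlying risk, event rates near 20% and 40%; 8,000 runs per setting (1,500 for the regression).

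| Approximate ρ | Chi-square | Matched-set Mantel-Haenszel | Logistic, adjusted for the matching score |
|---|---|---|---|
| 0.04 to 0.05 | 0.045, 0.044 | 0.048, 0.049 | 0.045, 0.053 |
| 0.14 to 0.17 | 0.039, 0.034 | 0.054, 0.055 | 0.057, 0.052 |
| 0.25 to 0.29 | 0.023, 0.024 | 0.047, 0.053 | 0.053, 0.050 |

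The unadjusted test is conservative, as the algebra predicts. A matched test stays near 5%, and so does a regression that contains the matching score.

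**5. How plausible is the range?** Assume beta-distributed risk, perfect matching and event rates of 20% to 40%. Then ρ = 0.05 corresponds to a score with an area under the ROC curve of about 0.63 to 0.66, and ρ = 0.30 to about 0.82 to 0.86. The top of the range needs a strong predictor.

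**The case against.** **The chi-square item is generic.** It applies properly to PUL v TURP/laser, which is unmatched, and does not name PUL v SNDS. This stands. The regression item does name PUL v SNDS, however, and it too makes no reference to the set.

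**Adjusted regression may already be sound.** The factor in step 2 is for a crude difference. If age, month and the risk score are among the potential confounders, the regressions are largely repaired (step 4). This stands as a condition: the protocol does not say whether they are included. It also does nothing for the crude tests or the log-rank.

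**A SAP is promised.** Covariate lists, robust variances and resampling units usually belong there, and naming linear or logistic regression does not exclude them. This is partly right, and it makes the repair easy. But the protocol does more than leave a gap: it states methods for independent groups and fixes a matched design.

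**Low consequence.** The comparison is secondary and much of section 11.2.4 is descriptive. This stands. The score predicts complications, so the correlation for costs or retreatment may be weaker.

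A reader might go further in three ways that the documents do not support:
- *More false positives.* With positive within-set correlation the error runs the other way: real alpha is below 5%.
- *The main result is unsafe.* The primary cost-effectiveness ratio (sections 4.2 and 11.2.3) compares the PUL and TURP/laser cohorts, which are not matched.
- *With 80 PUL patients, more controls could not make up the loss.* With m controls per PUL patient the independent-groups variance is (1 + 1/m)σ²/80, which falls towards σ²/80. That is below 1.2(1 − ρ)σ²/80 whenever ρ < 1/6, so at low correlation enough extra controls could offset the loss.

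**Conclusion.** The point holds as a mismatch of moderate size between design and named methods. For unadjusted PUL v SNDS comparisons, the independent-groups standard error is about 3% to 20% too large over an assumed ρ of 0.05 to 0.30. The lower part of that range is easier to reach with an ordinary score. Intervals are too wide and tests conservative. If ρ is near zero nothing material is lost. The adjusted regressions are affected only so far as they omit the matching variables. The figures assume complete 1:5 sets, a common variance and positive within-set correlation; none of these can be verified from the protocol. The consequence is confined to secondary PUL v SNDS results.

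**What to change.** In section 11.2.1, or in the SAP with a cross-reference:
- Restrict the independent-groups tests and the plain log-rank test to PUL v TURP/laser.
- For PUL v SNDS, keep the stated linear and logistic models, include age, month of procedure and the hDRS as covariates, and use standard errors clustered on matched set.
- For time to event in PUL v SNDS, use a Cox model with the same covariates and set-clustered variance.
- Where costs are bootstrapped for PUL v SNDS, resample whole matched sets. Section 11.2.1 calls for the bootstrap below 100 patients, which includes the PUL cohort of 80.

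Conditional logistic regression or a Cox model stratified on set would also respect the matching. They estimate a within-set effect rather than the one in the stated models, and they drop sets that carry no outcome information, so they can lose precision. They are not the first choice here.

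The cost is slightly more analysis work and a matched-set identifier kept in the analysis file, including through the random renumbering of patients described in section 14.3. No new data are needed.

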In addition to provide exhaustive information on the costs of all healthcare consumptions supported by the national healthcare system during the 3-year follow-up, which is very challenging by using conventional methods, the SNDS analysis will provide accurate statistical power to compare the PUL cohort to patients treated with each transurethral procedure. The SNDS analysis will also increase the generalizability of the study results by considering TURP/laser patients randomly selected from all French hospital centers, contrary to the clinical part of the study which will be focused on 7 investigational centers. The SNDS database will however not provide any clinical information on the functional results of the interventions thereby justifying to combine it with a conventional clinical study.

Incremental cost per avoided complication as main evaluation criterion

In this study, we propose an incremental cost / avoided complication at 4 months as the primary result for the following reasons:

- The incremental cost/Qaly is difficult to assess in our context: in France, only EQ-5D and HUI3 questionnaires have utility index that are validated in the French population. However, according to the literature and some experts, these questionnaires are too "generic" to really capture differences in quality of life between both groups of patients in the context of BOO. These questionnaires are not enough discriminating to propose a relevant cost/Qaly ratio as the main objective. However, this ratio will be provided as a secondary objective as it remains necessary for public decisions makers to know it in our French context.
- In our case, on a clinical point of view, avoided complication represent one of the most relevant criteria to discuss the place of PUL in the therapeutic strategy of BOO in comparison with transurethral surgery. We therefore chose the incremental cost / avoided complication at 4 months as the main evaluation criterion in this study.

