3.2. SECONDARY OUTCOMES MEASURES

Secondary endpoints will be:

- The incremental cost/Qaly of PUL compared to transurethral surgery at 12 months
- The total hospital cost of each surgery procedure based on a top down micro-costing method performed during hospitalization stay
- Overall and specific urogenital healthcare consumptions at 4 months, 1 year and 3 years following the surgical procedure
 - Dispensed medications identified using the corresponding codes of the Anatomical Therapeutic Chemical (ATC) Classification;
 - o In- and out-patient visits;
 - Hospitalisation and their corresponding discharge diagnoses coded according to International Classification of Disease, 10th revision;
 - Medical procedures;
 - Nursing acts and physiotherapy;
 - Medical imageries and lab tests;
 - Transport;
 - Sick allowances;
 - At 4 months: all healthcare consumptions which are not reimbursed, but payed by the patient (e.g.: urinary incontinence products).

• BPH retreatment,

• Any dispensing of the following medications at 1 and 3 years after surgical procedure: alpha-blockers (ATC code G04CA) or 5-alpha-reductase inhibitors (ATC code G04CB);

 Hospitalization at 1 and 3 years after surgical procedure, with the main diagnosis of BPH (ICD-10 code N40) and the surgical procedure codes JGNE003, JGNE171, JGNJ001, JGFA005 JGFA009, JGFA015, JGFE023, JGFE365.

Urinary symptoms,

- Urinary incontinence evolution between inclusion and 4 months after surgical procedure (Incontinence Severity Index (ISI));
- International consultation on Incontinence questionnaire for Urinary incontinence short form (ICIQ-UI SF)
- Hospitalization with a discharge diagnosis ICD-10 code related to an urinary infection (code N41 for acute prostatitis or code N10 for acute pyelonephritis) at 1 and 3 years after surgical procedure;
- Hospitalization with a discharge diagnosis ICD-10 code related to urinary retention (R33) at 1 and 3 years after surgical procedure;
- Hospitalization with a discharge diagnosis ICD-10 code and/or medical procedure related to urethral stricture at 1 and 3 years after surgical procedure.

• Global quality of life,

- IPSS and IPSS-Q8 evolution between inclusion, 4 month, and 1 year after surgical procedure;
- O Jenkins sleep questionnaire between inclusion, 4 months, and 1 year after surgical procedure;
- EQ-5D-5L questionnaire (appendix 2) evolution between inclusion, 4 months, and 1 year after surgical procedure;

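### Section 11.2.1 does not exempt costs from its Mann-Whitney rule, so an unadjusted secondary cost test can contradict the mean cost difference

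*Protocol*

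**What the plan says.** The general rule in section 11.2.1 is that the means of two independent groups are compared by Student's "t-test when normal distribution is followed (or Mann-Whitney's test when normal distribution is not followed"). The same section adds "For all tests, a 2-sided significance level of 5% will be used". The only provision there that is specific to costs concerns confidence intervals: "bootstrapping method for costs when count < 100 patients".

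Costs are among the outcomes to be compared. The secondary objectives in section 2.2 include the real cost of hospitalisation and healthcare consumption at 4 months, 1 year and 3 years. Section 3.2 lists "The total hospital cost of each surgery procedure based on a top down micro-costing method". Section 1.3 expects the claims database to give "exhaustive information on the costs of all healthcare consumptions supported by the national healthcare system during the 3-year follow-up".

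Three other provisions do work on means:
- Section 11.2.3 bootstraps the cost-effectiveness ratio and the net monetary benefit.
- The last bullet of section 11.2.1 uses linear regression for adjusted comparisons of quantitative variables.
- The data analysis part of the Summary uses linear regression for quantitative variables in the comparisons after 1 and 3 years.

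**The concern.** The bullet announces a comparison of means, but for non-normal data it names a test of ranks. Cost data are positive and usually skewed, so they fall on the Mann-Whitney side. A payer's budget depends on the arithmetic mean, and section 11.2.3 builds its ratio from the same quantity.

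Rank and mean answers agree when the two cost distributions have the same shape. The protocol gives reason to doubt that here. Section 1.1.2.3 puts implants at about €500 each with a mean of 4 per procedure, roughly €2,000 that almost every PUL patient incurs. Section 1.1.2.1 reports complications of grade 2 or higher in 20 to 40% of transurethral patients, and section 1.2 hopes that avoiding such events pays for the implants. If so, the saving lies in the upper tail of the comparator's costs, which ranks largely discount. A crude p-value could then mark PUL as dearer beside a mean difference of zero or in its favour, in a report meant to support reimbursement.

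**Working it through.** **Inputs from the protocol.** Section 11.1 gives "80 patients (in each of the PUL and TURP cohorts) will allow 95% confidence intervals with a precision" of 13% to 26% for means with coefficient of variation (CV) 0.6 to 1.2, and "400 patients in each of the 3 subgroups of the SNDS cohort" with 6% to 12%. Tests are two-sided at 5% (section 11.2.1).

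**The plan's own figure.** Relative half-width = 1.96 × CV / √n. For n = 80: 1.96 × 0.6 / 8.944 = 13.1% and 1.96 × 1.2 / 8.944 = 26.3%. For n = 400: 5.9% and 11.8%. All agree with section 11.1.

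**Assumptions.** The protocol gives no cost SD by group. The CV range above is generic: it is not specific to costs and assigns no value to either cohort. Below, true mean costs are equal, costs are lognormal, and CVs are varied within 0.6 to 1.2.

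**Does the rule route such costs to Mann-Whitney?** Yes. In simulated lognormal and gamma costs, a Shapiro-Wilk test rejected normality in at least one group in all 500 samples checked per scenario.

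**Why the rank test moves.** For a lognormal variable, log-variance = ln(1 + CV²) and median/mean = 1/√(1 + CV²), that is 0.857 at CV 0.6 and 0.640 at CV 1.2. Take PUL at 0.6 and TURP/laser at 1.2:
- Log-variances are 0.3075 and 0.8920.
- With equal means, the log-means differ by (0.8920 − 0.3075)/2 = 0.2923.
- P(PUL cost > TURP/laser cost) = Φ(0.2923 / √1.1995) = Φ(0.267) = 0.605, not 0.5.
- At 80/80 the null standard error of that probability is √(161 / (12 × 80 × 80)) = 0.0458, so z = 0.1052 / 0.0458 = 2.30. Approximate rejection is Φ(2.30 − 1.96) = 63%.

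**Simulation, two-sided Mann-Whitney rejection with equal true means.** Independent runs agree to about one percentage point.

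| CV PUL / CV TURP-laser | 80 vs 80 | 80 vs 400 |
|---|---|---|
| equal (0.6/0.6 or 1.2/1.2) | about 5% | about 5% |
| 0.9 / 1.2 | 19% | 27% |
| 0.6 / 0.9 | 26% | 37% |
| 0.6 / 1.2 | 63% | 90% |

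In the unequal rows almost every rejection calls PUL dearer. Gamma costs at 0.6 / 1.2 give 65% and 92%. With the CVs swapped at 80/80, Mann-Whitney calls PUL cheaper in 63%. With PUL truly 10% cheaper (0.6 / 1.2, 80/80) it still calls PUL dearer in 32%.

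**Tests of means in the same settings.** At 0.6 / 1.2 and 80/80, Welch rejects in about 6% and a percentile bootstrap in 7.7%. Over the settings examined the two range from about 5% to 8%.

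**Directly observed hospital cost.** Section 4.2 plans 5 patients per group and states a total of 30, while naming four sites. This gives 15 per group (30/2) to 20 per group (5 × 4). At 0.6 / 1.2, Mann-Whitney then rejects in about 15% to 22%.

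**The case against.** The strongest reply is that little rests on this test. In a non-randomised study the adjusted result carries the inference, and the protocol makes that a linear regression, which compares means. The ratio and net monetary benefit are bootstrapped. Cost intervals in both 80-patient cohorts are bootstrapped as well, and arithmetic means are always reported. Section 11.2.4 lists hospital cost as an estimation and consumption as a description, and names no test for either. All of this stands, and it confines the point to crude secondary p-values.

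The size is also open to challenge. The 63% and 90% figures place the two groups at opposite ends of a generic CV range. A reader might take 0.6 and 1.2 as the protocol's values for PUL and for TURP/laser, but section 11.1 makes no such assignment. Section 4.2 describes the surgery as fairly standardised, and with assumed CVs of 0.2 against 0.3 or 0.3 against 0.4 at 15 to 20 per group, rejection is about 5–6%. The 80-against-400 column cannot apply to micro-costed hospital stays, because the claims-database controls have no micro-costing.

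Two further inferences are tempting and not supported. The bullet is limited to independent groups and does not say that matched PUL and SNDS sets are analysed as independent; that handling can be set in the analysis plan. The limit of 100 patients governs intervals only, and no failure of the normal approximation at n = 400 has been shown.

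What the reply does not remove is the rule itself: it says means are compared, names a test that does not compare them, and leaves costs inside it.

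**Conclusion.** The point holds as a defect of a stated rule with limited reach. As written, section 11.2.1 would give skewed costs an unadjusted test that can contradict the bootstrapped mean difference and the cost-effectiveness ratio when the two cost distributions differ in shape. A reader might infer that the primary result or the 1- and 3-year cost conclusions are at risk. They are not, because those analyses use the bootstrap or linear regression.

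The size depends on group CVs that the protocol does not give. It runs from no inflation with equal shapes, through 19–26% at 80/80 for moderate contrasts, to 63% at the extreme of the range. Calling PUL dearer also requires the heavier tail to be in TURP/laser. That is plausible from the protocol's own reasoning but is not established, and the error reverses if PUL has the heavier tail. The correction is worthwhile because it is cheap and prevents two conflicting answers on the same cost.

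**What to change.** Add one sentence to section 11.2.1: cost variables, including costed healthcare consumption, are exempt from the normality and Mann-Whitney rule, and their arithmetic means are compared by bootstrap (or Welch test) whatever the sample size. Mann-Whitney can stay for symptom and quality-of-life scores.

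The bootstrap is already planned for the ratio and for cost intervals, so no new data, sample size or software is needed. The small downside is that the bootstrap and Welch test are only approximate for skewed costs at n = 80, with about 5–8% rejection at a nominal 5%. That is far nearer the stated level than Mann-Whitney when the shapes differ.
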